Prior to discharge from the cath lab, a formal neurovascular check should be performed for assessment of Impella-related limb ischemia. This can be performed either by an in-depth physical examination, peripheral angiogram, or lower extremities doppler studies. If signs of limb ischemia are noted, the peel-away sheath should be removed (if not already done so) with reassessment. If limb ischemia persists, antegrade access should be performed to provide distal lower extremity blood flow.

4. Post-PCI Hemodynamics

After the intervention is completed, right heart pressures, cardiac output, and CPO will be obtained. If CPO is > 0.6 , no further intervention is required. If CPO is ≤ 0.6 , right heart pressure will be reviewed to identify evidence of right ventricular failure if present (PAPi < 0.9).

If evidence of right ventricular failure are present (PAPi < 0.9), or if the Impella is suctioning, operators should consider right ventricular support with commercially available devices (Impella or Tandem Heart). Irrespective of CPO, evidence of RV shock is a warning not

to increase alpha agonists. These agents dramatically increase pulmonary vascular resistance (PVR) at a time of minimal RV reserve and can cause a lethal spiral as increasing doses of alpha agonists to maintain arterial pressure leads to decrease forward RV flow and worsens hypotension.

If CPO < 0.6 persists and RV shock is not the cause, consideration for the placement of an Impella 5.0 or a durable left ventricular assist device (LVAD) should be considered.

5. Weaning and Explantation

Impella devices should only be considered for explantation once the following criteria have been met:

1. Weaning of all inotropes and vasopressors
2. CPO > 0.6 watts without vasopressors or inotropes, and
3. PAPI > 0.9.

6. Safety and Monitoring

Cautious attention should be paid to the infrequent yet serious complication of limb ischemia with the use of large bore sheaths and devices. Detailed neurovascular checks should be performed while on Impella support. Use of antegrade sheaths to provide flow to the affected limb is strongly recommended in such cases. Prophylactic use antegrade access may also be considered, especially in patients who will likely require >24 hours of support. Although rare hemolysis can also occur, daily hemoglobin level should be obtained while on support. If there are signs of hematuria, Impella positioning should be checked via echocardiography.

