- Prior to discharge from the Cath Lab, a detailed vascular exam should be performed including femoral angiogram and Doppler assessment of the affected limb.
- If indicated, external bypass should be performed.

ICU Care

- Daily hemodynamic assessments should be performed, including detailed vascular assessment
- Monitor for signs of hemolysis and adjust Impella position as indicated

Device Weaning

Impella should only be considered for explantation once the following criteria are met:

- Weaning off from all inotropes and vasopressors
- CPO >0.6, and PAPI > 0.9

Bridge to Decision

Patients who do not regain myocardial recovery within 3-5 days, as clinically indicated, should be transferred to an LVAD/Transplant center. If patients are not candidates, palliative care options should be considered.

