Support was weaned according to: PA Sat Echo RHC Hemodynamics
 Other: _____

Total hospital duration (Days): _____

Left Ventricle Ejection Fraction (Pre-Impella): _____ (Prior to discharge): _____

DID THE PATIENT SURVIVE THE INDEX PROCEDURE? Yes No N/A

Was the patient transferred to VAD/Transplant Center Yes No N/A

 If "Yes", DID THE PATIENT SURVIVE TO TRANSFER? Yes No N/A

Did the patient have any additional support devices implanted post-index procedure? Yes No N/A

 If "Yes", which device was used: _____

DID THE PATIENT SURVIVE TO DISCHARGE? Yes No N/A

Was the patient discharged to hospice? Yes No N/A

Did the patient experience any significant Impella-related complications?

NO Vascular Complications Hemolysis

OTHER – Please explain: _____

Did the patient require any blood transfusions? No Yes – # of transfusions: _____

Was any external form of vascular bypass performed to provide lower extremity perfusion during Impella (i.e. antegrade access, "up and over" perfusion catheter, etc.)?

No Yes – Please Explain: _____

Please provide a brief description of the patient's hospital course (including significant complications and discharge circumstances):

Please Explain: _____

If the patient did not survive, please indicate the major cause of death (fatal bleeding, anoxic brain injury, worsening cardiogenic shock, patient/family wishes?)

Please Explain: _____

Cardiac Medications on Discharge (name only): _____

- END OF FORM -

APPENDIX 4
Patient Exclusion Form

National Cardiogenic Shock Initiative

PATIENT EXCLUSION FORM

(Version 2.0)

Please complete and email this form via [SECURE] email to: [contact].
Please email/call if there are any questions or concerns.

Hospital: _____

Hospital - City, State: _____

Physician: _____

Date: _____

Age: _____

Gender: Male Female Other

Race: White Black Hispanic Other

Patients will be excluded if there is at least one NO response to the inclusion criteria or at least one YES response to the exclusion criteria.

INCLUSION CRITERIA:

YES NO

- | | | |
|--------------------------|--------------------------|---|
|  |  | ACUTE MI: Symptoms with ECG and/or biomarker evidence of STEMI or NSTEMI |
|  |  | CARDIOGENIC SHOCK: Defined by the presence of at least two of the following: |

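### The CRF's cause-of-death item lists patient or family wishes among causes, so the underlying cause, and any part a device complication played, can go unrecorded

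*Protocol*

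**What the plan says.** The item stands near the end of the Case Report Form (Protocol, Appendix 3, Post Procedural Follow Up): "please indicate the major cause of death (fatal bleeding, anoxic brain injury, worsening cardiogenic shock, patient/family wishes". The bracket closes with a question mark, and an open line for explanation follows. There are no tick boxes and no code list.

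Higher in the same section, every patient is asked "Did the patient experience any significant Impella-related complications". The choices are "NO Vascular Complications Hemolysis" and an other category marked "Please explain". The form also asks "Did the patient require any blood transfusions", with the number given. It asks about external bypass for limb perfusion, hospice discharge (its own Yes/No), and a free-text account of the hospital course that is to cover complications.

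Appendix 1 bears on this in two places. On patients without myocardial recovery, the algorithm card says under Bridge to Decision: "If patients are not candidates, palliative care options should be considered". Section 6, Safety and Monitoring, says: "Cautious attention should be paid to the infrequent yet serious complication of limb ischemia with the use of large bore sheaths and devices". It also names hemolysis as a rare complication.

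The outcomes the protocol names are discharge survival and mortality at 1 and 12 months. The 30-day and 1-year forms (Appendices 5 and 6) ask about survival only.

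**The concern.** The item asks for one major cause but mixes two kinds of answer. Bleeding, anoxic brain injury and worsening shock say why the patient was dying. The wishes of the patient or family say how care ended. These are not exclusive: a patient with a major bleed whose family asks for support to stop fits two prompts, and the form gives no rule for choosing. A site that writes only that the family wished to stop has answered the item as worded.

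What is at stake is the link between a complication and a death. If that link is recorded at some sites and not at others, a table of causes of death or a count of device-related deaths would partly reflect how each site fills in the line. The plan foresees about 75 sites and a device-based strategy, and Analysis and Publication of Data commits to publishing all data.

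**Working it through.** The plan states no figure on this point, so there is none to reproduce. The check is a reading of the form, followed by arithmetic for scale only.

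**Reading the form**

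1. *Can the item be completed without an underlying cause?* Yes. One of the four prompted answers is not a cause, and nothing asks for the cause when that answer is given.
2. *Does another structured field supply the link to death?* No. The complications item has no bleeding box and does not ask whether the complication contributed to death. A transfusion count does not attribute a death. Hospice discharge has a Yes/No, but withdrawal of support before an in-hospital death does not.
3. *Are the device harms of Appendix 1 prompted as causes?* Limb ischemia and hemolysis are not among the death prompts. They can be recorded in the complications item, under vascular complications and hemolysis.
4. *Can free text supply the link?* Yes, in the explanation line or the hospital-course narrative, if the site writes it there.
5. *Is a named outcome affected?* No. Discharge survival and 1- and 12-month mortality are all-cause.

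**Scale**

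Inputs from the protocol: about 500 patients to be approached (Population and Eligibility Criteria), 76% survival to discharge in the 41-patient pilot (background), and a target above 80% (algorithm card, quality measures). Treating all 500 as enrolled is an assumption.

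- In-hospital deaths at pilot survival: 500 × (1 − 0.76) = 120.
- In-hospital deaths at 80% survival: 500 × (1 − 0.80) = 100.

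Let *h* be the share of deaths truly due to bleeding or device harm, and *w* the share of those recorded only as wishes. The documents give neither. Assume *h* = 5–20% and *w* = 10–50%.

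- Lost attributions = deaths × *h* × *w*.
- Low end: 120 × 0.05 × 0.10 = 0.6 (0.5 with 100 deaths).
- High end: 120 × 0.20 × 0.50 = 12 (10 with 100 deaths).
- With *w* = 0: none.

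The harm share among all deaths would read *h*(1 − *w*) instead of *h*. With *h* = 10% and *w* = 50%, 12/120 = 10% (Wilson 95% CI 5.8–16.7%) would read as 6/120 = 5% (2.3–10.5%).

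**Direction**

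Deaths from shock or anoxic injury can also be entered as wishes. Let *v* be the share of those so recorded (assumed 20–40%). With *h* = 10% there are 12 harm deaths and 108 others. Among deaths with a stated cause, the harm share is 12(1 − *w*) / [12(1 − *w*) + 108(1 − *v*)].

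- *w* = 50%, *v* = 20%: 6 / (6 + 86.4) = 6.5%.
- *w* = 10%, *v* = 40%: 10.8 / (10.8 + 64.8) = 14.3%.

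So with all deaths as denominator the harm share can only fall or stay the same. With only deaths of stated cause as denominator, it can move either way.

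**The case against.** The strongest reply is that the item is not a closed choice. The bracketed terms are prompts for a free-text line, and a careful site can write both the bleed and the withdrawal of care. The same part of the form records vascular complications, hemolysis, other complications, transfusions and a narrative, so deaths can be cross-tabulated with recorded harm. Coding of free text could be settled in the statistical analysis plan, which is not shown. No cause-specific mortality outcome is named. The palliative pathway in Appendix 1 concerns patients without myocardial recovery and does not show that bleeding or limb-ischemia deaths take that route.

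All of this stands, and it limits the point. It does not remove it. A cross-tabulation shows that a complication and a death occurred in the same patient, not that one led to the other. Coding at analysis cannot recover a link that a site did not write down, and the form suggests an answer that omits it.

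A reader might infer that fatal harm is undercounted, or that its share is biased downward. The documents do not support that. They show that the link can be lost. They do not show that it is, how often, or in which direction every summary would move.

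**Conclusion.** The item can misclassify cause of death, and no structured field ties a recorded complication to the death. A cause-of-death or device-related-death tabulation drawn from it could be unreliable, could understate fatal harm and may not be comparable across sites. The size is unknown. The range of 0.6 to 12 lost attributions among 120 deaths rests on assumed values of *h* and *w*, on full enrolment of 500 and on survival in a 41-patient pilot, and it is zero if sites use the explanation line fully. The harm event is not necessarily lost, and all-cause survival and mortality do not change. Severity: minor. This is a matter of data capture and touches no clinical rule.

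**What to change.** Remove patient or family wishes from the list of causes and record three items for each in-hospital death:

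- **(a) Underlying cause of death:** bleeding; limb or vascular complication; hemolysis; anoxic brain injury; cardiogenic shock; other (specify).
- **(b) Support withdrawn on patient or family wishes:** Yes/No.
- **(c) A recorded complication contributed to the death:** Yes/No.

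Keep the explanation line. For forms already received, code these items from the existing free text where it allows, and otherwise enter not determinable. Report (a) cross-tabulated with (b), and show the number not determinable.

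The cost is one CRF revision with the matching REDCap fields, and some recoding of narratives. Harm-related deaths may appear more frequent in the report than they would under the present item.

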From this data, the following Quality Metrics will be tracked:

- Discharge survival
- Duration of shock-to-support times

- Use of Impella Support pre-PCI
- Use of right heart catheter for hemodynamic monitoring
- Attainment of TIMI III flow post reperfusion
- Attainment of Cardiac power > 0.6 watts after completion of therapy
- Reduction or elimination of vasopressors and inotropic agents.

Population and Eligibility Criteria

Due to the heterogeneous cohort of patients who present with AMICS, we have defined a specific subset of patients from whom outcomes are to be collected. Approximately 500 adult patients will be approached to participate in the registry at approximately 75 sites in the United States. The duration of hospital participation in this research study is anticipated to be approximately 3 years.

Registry Inclusion Criteria

1. Symptoms of acute myocardial infarction (AMI) with ECG and/or biomarker evidence of S-T elevation myocardial infarction (STEMI) or non-S-T elevation myocardial infarction (NSTEMI)
2. Cardiogenic shock is defined as the presence of at least two of the following:
 - a. Hypotension (systolic blood pressure ≤ 90 mm Hg, or inotropes/vasopressors to maintain systolic blood pressure ≥ 90 mmHg)
 - b. Signs of end organ hypoperfusion (cool extremities, oliguria or anuria, or elevated lactate levels)
 - c. Hemodynamic criteria represented by a cardiac index of < 2.2 L/min/m² or a cardiac power output ≤ 0.6 watts.

3. Patient is supported with an Impella
4. Patient undergoes PCI

Registry Exclusion Criteria

1. Evidence of Anoxic Brain Injury
2. Unwitnessed out of hospital cardiac arrest or any cardiac arrest in which return of spontaneous circulation (ROSC) is not achieved within 30 minutes
3. IABP placed prior to Impella
4. Septic, anaphylactic, hemorrhagic, and neurologic causes of shock
5. Non-ischemic causes of shock/hypotension (pulmonary embolism, pneumothorax, myocarditis, tamponade, etc.)
6. Active bleeding for which mechanical circulatory support is contraindicated
7. Recent major surgery for which mechanical circulatory support is contraindicated
8. Mechanical complications of AMI (acute ventricular septal defect (VSD) or acute papillary muscle rupture)
9. Known left ventricular thrombus for which mechanical circulatory support is contraindicated
10. Mechanical aortic prosthetic valve
11. Contraindication to intravenous systemic anticoagulation

Risks/Benefits of and Alternatives to Patient Participation

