The diagnosis of AMI is confirmed by electrocardiographic changes indicative of new or presumed new ischemia (new ST-T wave changes), detection of elevated cardiac biomarkers or angiographic findings of an infarct related artery on coronary angiogram in the presence of ischemic symptoms.

Cardiogenic shock is defined as the presence of at least two of the following:

1. Hypotension (systolic blood pressure ≤ 90 mm Hg, or inotropes/vasopressors to maintain systolic blood pressure ≥ 90 mmHg)
2. Signs of end organ hypoperfusion (cool extremities, oliguria or anuria, or elevated lactate levels)
3. Hemodynamic criteria represented by a cardiac index of < 2.2 L/min/m² or a cardiac power output ≤ 0.6 watts.

2. Access, Baseline Invasive Hemodynamics

Due to the heterogeneous cohort of patients who present with AMICS, any diagnostic steps to ensure the presence of AMI or CS are left to the discretion of the primary operator (ie: timing of right heart catheterization, coronary angiogram and placement of MCS). We do recommend obtaining femoral access to ensure adequate vessel size for MCS. If a right heart catheterization has not been performed prior to MCS placement we recommend measuring a LVEDP prior to placement of MCS. In the event a LVEDP ≤ 15 mmHg, an alternate diagnosis should be suspected and right heart catheterization should be performed prior to MCS to confirm presence of cardiogenic shock. Following placement of large-bore access and administration of systemic anticoagulation an Impella catheter will be inserted and manipulated to obtain maximum

forward flow. Right heart catheterization (RHC) will be performed for calculation of cardiac power output (CPO), SVR and PCWP/RA ratio and pulmonary artery pulsatility index (PAPi), during the index procedure.

3. Intervention

PCI of the culprit lesion(s) should be performed, per national recommendations. We recommend against non-culprit PCI unless flow is impaired in the involved artery (ie. less than TIMI 3 flow and excluding chronic total occlusions); however the ultimate decision of multi-vessel PCI lies with primary operator. PCI can be performed with thrombectomy if a heavy thrombus burden is present. Once appropriately sized stents have been implanted angiography will be performed to assess TIMI flow. If TIMI III flow is not present, intracoronary vasodilatory should be administered at the discretion of the primary operator.

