** QUALITY MEASURES **

- Impella Pre-PCI
- Door to Support Time < 90 minutes
- Establish TIMI III Flow
- Right Heart Cath
- Wean off Vasopressors & Inotropes
- Maintain CPO >0.6 Watts
- Improve survival to discharge to >80%

NATIONAL CARDIOGENIC SHOCK INITIATIVE

[contact]

www.henryford.com/cardiogenicshock

NationalCSI - Algorithm - v1.5 - 11/2017

APPENDIX 2

Adoption of the NCSI Treatment Algorithm & Joining the NCSI

Adoption to the NCSI treatment algorithm is completely voluntary. Deviation from the treatment algorithm can occur without consultation of the primary investigators at the discretion of the primary operator. All AMICS patients, including those with treatment algorithm deviation, can be included in the NCSI registry as there is no formal, nationally accepted or standardized protocol or treatment algorithm for treatment of AMICS. Operators and hospitals are encouraged to review the pilot study data and treatment algorithm to determine if they wish to adopt the NCSI treatment algorithm as their standard of care for the treatment of AMICS.

Multi-hospital collaboration is considered a cornerstone to the success of the NCSI. We are reaching out nationally and encouraging hospitals to work together to collect data and demonstrate the success of regional shock protocols and/or treatment algorithms. Hospitals joining the NCSI group voluntarily agree to share data, post-discharge, including demographics, procedural characteristics and outcomes as detailed in the case report form. Data is de-identified and HIPAA-compliant. Data generated from the index procedure admission to discharge (or death, if prior to discharge) will be collected retrospectively and de-identified. Prior to discharge, surviving patients will be asked to consent to the collection of data at 30 days and 1 year post-index procedure. This data collection can occur via follow up phone call, electronic chart review, or any other method that complies with the site's SOPs.

To formally join and affiliate with NCSI, we request the minimum following requirements of the interested hospitals:

1. Implantation of >10 Impella per year (for any indication)

2. Adoption of the NCSI treatment algorithm as standard of care for patients who present with AMICS
3. Identification of a local Primary Investigator (PI) to coordinate data collection

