Door to Support Time (minutes): _____

Door to Balloon Time (minutes): _____

Procedural Characteristics (please circle the best choice, if answer is not known please write "N/A")									
Impella Placement:		1. Prior to PCI		2. Post PCI		3. Intra-procedural			
RHC Placement:		1. Prior to Impella		2. Post Impella		3. No RHC obtained			
Impella Used:			Impella Access:			AMI Type?			
2.5 CP 5.0 RP Other: _____			 Femoral  Axillary  Other: _____			STEMI NSTEMI			
PCI Attempted?	TIMI FLOW		Evidence of Thrombus Pre-PCI?	# of Diseased Vessels?	# Vessels Treated?	# of Stents?	Culprit Lesion(s) Location(s)		Other Lesion(s) Location(s)
YES	Pre-PCI	Post-PCI					1. LM	5. Ramus	1. LM 5. Ramus
NO	0	0		0	0		2. LAD	6. SVG	2. LAD 6. SVG
Successful?	1	1	YES	1	1		3. LCx	7. LIMA	3. LCx 7. LIMA
YES	2	2		2	2		4. RCA	8. RIMA	4. RCA 8. RIMA
NO	3	3	NO	3	3				
Access for PCI?	Was complete revascularization performed?		Thrombectomy used?	Atherectomy used?	PCI Complications?  NO  YES				
1. Radial	YES NO		YES NO	YES NO	If YES:  Stent Thrombosis				
2. Femoral	YES NO		YES NO	YES NO	 Evidence of Residual Thrombus				
	YES NO		YES NO	YES NO	 OTHER: _____				
Was patient taking antiplatelet medication at home?  No  Aspirin  Clopidogrel  Ticagrelor  Prasugrel  N/A									
 OTHER: _____									
Was patient loaded with antiplatelet prior to PCI:  No  Aspirin  Clopidogrel  Ticagrelor  Prasugrel  Cangrelor  Abciximab									
 Eftifibatide  Tirofiban  N/A  OTHER: _____									
If oral antiplatelets were given, what route were they given?  By Mouth  NG/OG Tube  Rectal  N/A  Other: _____									
Was the oral antiplatelet crushed?  Yes  No  N/A									

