| |  | Hypotension: Systolic blood pressure \leq 90mm at baseline, or use of inotropes or vasopressors to maintain SBP \geq 90 |
| |  | Evidence of end organ hypoperfusion (cool extremities, oliguria or anuria, or elevated lactate levels) |
| |  | Hemodynamic criteria: Cardiac index of $<$ 2.2 L/min/m ² or a cardiac power output \leq 0.6 watts. |
|  |  | Patient is supported with Impella |
|  |  | Patient undergoes PCI |

Continued on next page →

FOR HFH USE ONLY

NCSI #: _____

EXCLUSION CRITERIA:

YES NO

- Evidence of Anoxic Brain Injury
- Unwitnessed out of hospital cardiac arrest or any cardiac arrest in which ROSC is not achieved in 30 minutes
- IABP placed prior to Impella
- Septic, anaphylactic, hemorrhagic, and neurologic causes of shock
- Non-ischemic causes of shock/hypotension (*pulmonary embolism, pneumothorax, myocarditis, tamponade, etc.*)
- Active Bleeding
- Recent major surgery
- Mechanical Complications of AMI
- Known left ventricular thrombus
- Patient who did not receive revascularization
- Mechanical aortic valve
- Patient refused to sign consent for 1M & 1Y follow-up

Notes:

Completed by:

SIGNATURE

NAME (PRINTED)

DATE

APPENDIX 5
30 Day Follow-Up Form

National Cardiogenic Shock Initiative
30 Day Follow-Up
(Version 1.0)

Upon completion, please email this form via [SECURE] email to: [contact].
Please email/call if there are any questions or concerns.

NCSI #: _____

Hospital: _____

Hospital - City, State: _____

Date of Impella Implant: _____

Date of Follow-Up: _____

Patient Follow-Up – ≥ 30 Days from Date of Impella Implant:

Did the patient survive to 30 Days?

- YES
- NO
- Unknown
- Patient Unavailable
- Refused
- Other: _____

Point of Contact for Follow-up:

Patient Spouse LAR/Proxy Other: _____

Method of Follow-up:

- Phone Call
- Electronic Medical Record Review (patient signed-in for visit with ID at 30 or more days)
- Mail
- Email
- Other: _____

NOTES: _____

Follow-up performed by: _____

Title: _____

Signature: _____ Date: _____

APPENDIX 6
1 Year Follow-Up Form

National Cardiogenic Shock Initiative

1 Year Follow-Up

(Version 1.0)

Upon completion, please email this form via [SECURE] email to: [contact].
Please email/call if there are any questions or concerns.

NCSI #: _____

Hospital: _____

Hospital - City, State: _____

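### The algorithm card and the Patient Exclusion Form add an undefined no-revascularization exclusion that the protocol body lacks; a site can apply it to attempted PCI that restored no flow

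*Protocol*

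**What the plan says.** Registry Inclusion Criteria, item 4, reads "Patient undergoes PCI". It sets no condition on the result. The Registry Exclusion Criteria list 11 items, none about revascularization.

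The one-page algorithm card in Appendix 1 and the Patient Exclusion Form in Appendix 4 both list a further exclusion: "Patient who did not receive revascularization". Neither says what counts as receiving revascularization, and nor does the rest of the protocol. The form also repeats the PCI inclusion line. Its header says that a patient is out with one NO to an inclusion criterion or "at least one YES response to the exclusion criteria".

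The quality metrics include "Discharge survival" and "Attainment of TIMI III flow post reperfusion". The case report form (Appendix 3) has a yes/no field "PCI Attempted", a separate yes/no field for success, and post-PCI TIMI flow graded 0 to 3. The Intervention step of the treatment algorithm tells operators what to consider "If TIMI III flow is not present" after stenting.

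**The concern.** If the added line is applied to a PCI that was tried and failed, registry entry depends on the procedural result, and that result is one of the registry's own quality metrics. The patients removed cannot have attained TIMI III flow and would be expected to survive less often, so both metrics would move in the favourable direction.

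The timing makes this more than a matter of wording. Patients are approached after treatment, and hospitals share data after discharge (Research Procedures; Appendix 2). Each of about 75 sites would therefore settle the ambiguity with the procedural result, and often the survival outcome, already known. An analysis plan could define denominators, but it could not restore patients for whom no case report form was completed.

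**Working it through.** **1. One patient, three texts.** Take a patient on Impella whose culprit lesion could not be crossed, so that no flow was restored.

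| Text | Relevant line | Result |
|---|---|---|
| Protocol body | PCI undergone: yes; no exclusion applies | Eligible |
| Exclusion Form, line read as no PCI performed | Inclusion YES, exclusion NO | Eligible |
| Exclusion Form, line read as no revascularization achieved | Inclusion YES, exclusion YES | Excluded |
| Algorithm card | No PCI inclusion line; exclusion open to both readings | Eligible or excluded |

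On the form, the narrow reading (no PCI performed) makes the line redundant, because a NO to the PCI inclusion line already excludes. A coordinator could reasonably infer that it must mean something further. On the card the narrow reading is the more natural one, because the card has no PCI inclusion line and the exclusion can stand in for it.

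**2. Who is at risk.** A patient who was stented and left with TIMI 1 or 2 flow received revascularization and stays in under either reading. Only PCI that achieved no revascularization can be lost.

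**3. Illustrative size.** The protocol states no figure that depends on this point, so there is nothing to reproduce. All inputs here are assumptions: failed share of attempted PCI f = 3% to 8%; survival after failure 30%; survival among all attempts 72%; TIMI III among all attempts 85%; no failure attains TIMI III; every site drops every failure.

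- Survival with failures dropped = (0.72 − 0.30f) / (1 − f)
  - f = 0.03: 0.711 / 0.97 = 73.3% (+1.3 points)
  - f = 0.08: 0.696 / 0.92 = 75.7% (+3.7 points)
- TIMI III with failures dropped = 0.85 / (1 − f)
  - f = 0.03: 0.85 / 0.97 = 87.6% (+2.6 points)
  - f = 0.08: 0.85 / 0.92 = 92.4% (+7.4 points)

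If only a fraction g of failures is dropped, f is replaced by g × f and every shift shrinks. The figures above are the g = 1 limit.

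**4. Sensitivity to the assumptions.** Now anchor on the pilot's 76% discharge survival as the figure with failures dropped. With f from 2% to 10% and survival after failure (s) from 60% down to 20%, survival with failures kept is (1 − f) × 0.76 + f × s.

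- f = 0.02, s = 0.60: 75.7%, an inflation of 0.3 points
- f = 0.05, s = 0.40: 74.2%, an inflation of 1.8 points
- f = 0.10, s = 0.20: 70.4%, an inflation of 5.6 points

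**5. Scale.** The pilot survival is 76%, and the card's aim in percent is "Improve survival to discharge to >80", a gap of about 4 points. The 95% half-width for 76% in 500 patients is 1.96 × √(0.76 × 0.24 / 500) = 3.7 points. At the upper end of the assumptions the shift is of that order; at the lower end it is well inside it. Sampling error does not cancel a shift that runs in one direction only.

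**The case against.** A reader might infer that the form excludes failed PCI, so that body and appendices contradict each other outright. The documents do not support that. No passage says failed PCI is excluded, and the added line can be read as the negative of the PCI inclusion criterion. On that reading body, card and form agree. The case report form, with its success field and post-PCI TIMI grades down to 0, suggests that failures are meant to be recorded. It also allows NO to the attempt field, so its fields alone do not settle eligibility. Appendix 2 further says that patients with algorithm deviations can be included. All of this stands, and it limits the point to an ambiguity.

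A reader might also infer that the TIMI III metric loses its failures generally. It does not, since stented patients with TIMI 1–2 flow stay in. The 92.4% figure removes 8 of the 15 percentage points of patients without TIMI III, more than half, and needs every site to take the wide reading. It is a worst case under its assumptions.

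Lastly, the Exclusion Form logs its reasons, so removals would be visible, and a YES to both lines would identify them. That helps in counting them. It does not repair the metrics, because the form has no field for TIMI flow or survival.

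**Conclusion.** The point holds as an eligibility ambiguity with a one-directional consequence. Two appendix documents carry an exclusion that the body lacks, its key term is undefined, and one workable reading on the Exclusion Form removes attempted PCI that restored no flow after the result is known. The documents do not show that any site reads it that way.

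The direction of bias is upward for TIMI III attainment, and upward for discharge survival provided failed PCI carries lower survival. Its size cannot be derived from the protocol. The upper limits of 73.3–75.7% against 72% for survival, and 87.6–92.4% against 85% for TIMI III, rest wholly on the assumed rates and on complete dropping of failures. The change is worth making because it is nearly free and the lost records could not be recovered later.

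**What to change.** - On the algorithm card and the Patient Exclusion Form, replace the line with one saying that PCI was not attempted. On the form it could simply be deleted, because a NO to the PCI inclusion line already covers it.
- In the Registry Inclusion Criteria, state that attempted but unsuccessful PCI is eligible.
- State beside the quality metrics that these patients stay in the denominators for TIMI III attainment and discharge survival. This fits the attempt, success and post-PCI TIMI fields already on the case report form.
- Review any Exclusion Forms already received with YES to both the PCI inclusion line and the revascularization line, and count them.

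The cost is one line on two documents and a sentence or two in the body. Reported TIMI III and survival rates may be slightly lower than they would otherwise have been.
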